4.4.2 Patient Follow Up

Follow-up in all patients will occur at 3, 6, and 12 months following randomization during the first year and every 6 months thereafter, with clinic visits, phone follow-up, and other testing as described below. Economic and QOL data, including a full follow-up questionnaire of validated scales, ie, SF-36, DASI, Toronto Atrial Fibrillation Severity Scale, AF Effects on QOL (AFEQT), Work Productivity and Activity Impairment Instrument (WPAI), Stanford Presenteeism scale, will be repeated by trained telephone interviewer staff from the EQOL Coordinating Center (EQOL CC) for patients enrolled in North America and by the Site Coordinator in sites outside North America.

Follow-up visits/calls at 3 and 6 months should be completed within 30 days +/- of the due date (Ex: 3 month visit: completed between 60 days and 120 days of randomization).

Follow-up visits/calls at 12 months and every 6 months thereafter should be completed within 60 days +/- of the due date (Ex: 12 month visit: completed between 300 days and 420 days of randomization).

Medical bills for patients enrolled at US sites will be collected throughout the trial by the EQOL Coordinating Center economic team. The Site Coordinators will complete a one page Rapid Report Form (RRF) at each CABANA study visit documenting any interim hospitalizations and/or ER visits since last contact. These forms will be forwarded to the EQOL Coordinating Center for processing. As part of the economic and QOL data in CABANA, two EQ-5D forms that rate the patient's health by using a 0-100 "thermometer", asking 5 brief questions and Mayo Atrial Fibrillation Symptom Index (MAFSI) will be collected by the Site Coordinator at 3 and 12 months following randomization during the first year and yearly thereafter throughout the trial and entered into the e-CRF.

After enrollment, subjects will either receive a single 'CABANA Box' recording system to be used throughout the entire study, or will be followed using ambulatory event and Holter ECG monitoring as generated during the course of routine clinical care as dictated by their attending physician.

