7.3 Missing Data

Missing data will be handled differently for covariates and endpoints. Data for covariates (see Section 8.1) are expected to be complete or near complete for all patients. Where missing data do occur, using single-imputation methods, continuous variables will be imputed using the median value and categorical variables will be imputed using the mode.

Most primary and secondary endpoints are time-to-event analyses which rely on the ability to calculate the time from randomization (or in some cases time from the end of the 90-day blanking period) to when the event occurred or the date of last contact for censored individuals. Here, missing data may occur when: 1) a visit form or question that indicates if an event occurred (or not) is not completed, and 2) a form or question indicates that an event occurred, but

the event date is missing. The first category prevents the assignment of whether an event occurred or not, while the second category prevents calculation of time to the event. In all analyses, we consider only non-missing data in the determination of whether or not an event occurred (i.e., cases in category 1 will not be considered). Time-to-event for known events when the event date is missing (category 2), will be assigned based on the visit with which the event is recorded. For example, if the event is reported on the month 3 visit, then the time to event would be set to 91.26 days ($365/12 * 3$). If the event is reported on the month 6 visit, then the time to event would be set to 182.52 days ($365/12 * 6$), and so on for all visits up to month 96. If patients do not experience an event, and have an event-free status associated with a visit but no visit date on their last known visit, they will be assigned a censor date in the same manner. For patients with multiple events including a death, any imputed non-death event dates (e.g., cardiovascular (CV) hospitalization) will be forced to occur before the date of death.

If an event or censored status is reported, but both the visit number and event/censored date are missing, then the date of event/censor will be imputed using relevant data and considered on a case-by-case basis.

8. Primary Endpoint Analysis

Primary Endpoint: Time from randomization to the first event among a composite of major clinical outcomes consisting of

- Death (all-cause)
- Disabling stroke
- Serious bleeding
- Cardiac arrest

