9.8 Recurrent Atrial Fibrillation

Endpoint definition: This particular outcome will be analyzed with different endpoint definitions in order to provide an overall perspective of the extent of the AF burden experienced by the study subjects. The first analysis will consider the first episode of recurrent AF as the endpoint, defined as an episode ≥ 30 seconds following the end of the 90-day blanking period, where the 90-day blanking period begins at the time of receiving the randomly assigned treatment (either ablation or drug therapy). The endpoint will be defined as the time until the first recurrence of AF according to this definition. Similar analyses will be performed where the endpoint is defined as: (a) an episode of *symptomatic* recurrent AF, (b) an episode of atrial fibrillation or atrial flutter or atrial tachycardia, and (c) an episode of *symptomatic* atrial fibrillation, atrial flutter, or atrial tachycardia.

Analysis Population: Because recurrent atrial fibrillation is defined with respect to the end of the blanking period, which begins after receipt of the assigned treatment, all analyses for recurrent atrial fibrillation will include only patients who have received their randomly assigned treatment and live to the end of the blanking period.

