Using the methods described for the primary endpoint in Section 8, an analysis will also be performed to compare the primary endpoint and the key secondary clinical outcomes of the two treatment strategies among the subset of patients who fully satisfied the inclusion/exclusion criteria and received the treatment to which they were randomly allocated. This analysis will include patients randomized to the drug arm who were treated with drug therapy, and patients randomized to the ablation arm who underwent the ablation within 6 months following enrollment in the trial. The follow-up of drug-arm patients who crossed over to ablation will be censored at the time of the ablation. Patients randomized to the ablation arm who were not ablated within 6 months will be excluded from this analysis. Additional sensitivity analyses will be performed in which the window for ablation is varied to include a shorter interval (3 months) and a longer window (1 year).

The analyses outlined in Sections 10 and 11 will be strictly supplementary to the intent-to-treat analyses described earlier.

12. Multiple Comparisons

With the primary hypothesis and the various secondary endpoints that have been outlined, there is a multiplicity of analyses to be performed, which leads to an increased probability that at least one of the comparisons could be "significant" by chance. There are adjustments (e.g., based on the Bonferroni inequality) that could be used to preserve the overall type I error level. To attempt to adjust for the effects of the repeated significance testing that will occur as part of the interim monitoring (discussed below), plus adjust for the multiplicity of secondary endpoints, would require that very small significance levels be used for every comparison. The overall level of significance will be 0.049 for the assessment of the primary endpoint (see Section 13) and 0.05 for all secondary endpoints. However, to account in part for the multiplicity of comparisons involving secondary endpoints, we will be conservative in the interpretation of the analyses, taking into account the degree of significance, and looking for consistency across endpoints. The actual p-value for each comparison will be reported to aid in the overall interpretation. We have

also pre-specified the primary and secondary outcome variables to avoid over-interpretation of strictly exploratory comparisons.

13. Interim Analyses

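### SAP 7.3 times an undated event at the nominal month of the reporting visit even when the visit date is known, so the event can be placed after the visit that reported it

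*SAP*

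**What the plan says.** SAP 7.3 deals with events known to have occurred but lacking a date. The time to such an event "will be assigned based on the visit with which the event is recorded". The worked example is that "if the event is reported on the month 3 visit, then the time to event would be set to 91.26 days"; month 6 gives 182.52 days, and the same pattern runs to month 96. The actual date of the visit plays no part.

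The section treats censoring differently. The nominal month applies only to patients who "have an event-free status associated with a visit but no visit date on their last known visit". The one ordering limit on imputed event dates is that "any imputed non-death event dates (e.g., cardiovascular (CV) hospitalization) will be forced to occur before the date of death". No limit is set at the reporting visit or at last contact. The section covers endpoints measured as "time from randomization (or in some cases time from the end of the 90-day blanking period").

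Protocol 4.4.2 allows 30 days either side of the due date at months 3 and 6, and 60 days either side from month 12 on. Its own example is "12 month visit: completed between 300 days and 420 days of randomization".

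Two later parts of the SAP use the order of an event and an ablation. In Section 10 a time-dependent variable switches to ablation when a drug-arm patient is ablated. In Section 11 (per-protocol), "The follow-up of drug-arm patients who crossed over to ablation will be censored at the time of the ablation".

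**The concern.** An event reported at a visit must have happened after the previous contact and no later than that visit. Both limits are usually known. The SAP rule discards them and uses a calendar point that can lie outside the interval. An event can then be timed after it was already on record, or after the patient's last contact. Because the visit date is honoured for censoring but not for events, the two halves of the rule are also inconsistent.

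The endpoints most exposed rest on site-reported hospitalization. SAP 7.3 itself names cardiovascular hospitalization as an imputed event, and SAP 9.2 and 9.3 take the cause of hospitalization from the site. It enters secondary endpoints 2, 3 (heart failure and acute ischemic admissions) and 9. A shift of weeks matters little to a log-rank comparison over several years, but it matters more where the analysis depends on whether the event came before or after an ablation.

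**Working it through.** **The plan's own figure.** 365/12 × 3 = 91.25 and 365/12 × 6 = 182.50. The stated 91.26 and 182.52 follow if the month is first rounded to 30.42 days (30.42 × 3 = 91.26; 30.42 × 6 = 182.52). The difference is immaterial.

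**How far the assigned time can pass the reporting visit.** Overshoot = assigned day minus earliest in-window visit day. Months 3 and 12 use the windows printed in Protocol 4.4.2. Months 6 and 18 apply its 30-day and 60-day allowances to 182.5 and 547.5 days.

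| Visit | Assigned day | Earliest in-window day | Overshoot (days) |
|---|---|---|---|
| Month 3 | 91.26 | 60 | 31.26 |
| Month 6 | 182.52 | 152.5 | 30.02 |
| Month 12 | 365.04 | 300 | 65.04 |
| Month 18 | 547.56 | 487.5 | 60.06 |

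If month 3 visits were spread evenly over days 60 to 120 (an assumption), (91.26 − 60)/60 = 52% of them would precede the assigned day.

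**On-time visits.** The rule places the event at the end of its interval. If true dates are uniform over the interval (an assumption), mean lateness is 91.25/2 = about 45 days at months 3 and 6, and 182.5/2 = about 91 days at six-month intervals.

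**Late visits.** The error can also run the other way. An event just before a month 12 visit on day 420 is timed 420 − 365.04 = about 55 days early.

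**Crossover example (days chosen for illustration).** A drug-arm patient's undated event is recorded at a month 12 visit on day 300. The patient is ablated on day 320. The rule times the event at day 365.
- On-treatment (SAP 10): the ablation variable has been 1 since day 320, so an event that preceded ablation is charged to ablation. All three constructions of the variable treat a drug-arm crossover this way.
- Per-protocol (SAP 11): follow-up was censored on day 320, so the event is lost.
- With the event capped at day 300, both analyses keep it in drug-arm time.

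**Recurrent AF.** SAP 9.8 defines recurrence after a 90-day blanking period, "where the 90-day blanking period begins at the time of receiving the randomly assigned treatment (either ablation or drug therapy"). If treatment starts s days after randomization, day 91.26 lies after blanking only if s + 90 < 91.26, that is, s < 1.26. A start on day 0 puts the episode 1.26 days into the at-risk period. A start on day 2 or later leaves it inside blanking; a start on day 14 means blanking ends on day 104.

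**The case against.** The strongest reply is that this hardly matters. The rule is identical in both arms. Primary-endpoint events have dedicated event forms and blinded adjudication, so few should lack a date. Protocol 4.4.2 calls for follow-up data at crossover and when an endpoint emerges, which limits how often an undated event can drift past an ablation. The analyses in SAP 10 and 11 are declared strictly supplementary. All of this stands and bears on size. It does not justify a rule that ignores a known visit date and can return an impossible one.

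A reader might go further and infer that the rule turns undated AF episodes from the blanking period into recurrences on about the first day at risk, mainly in the drug arm, because drugs start at once and ablation comes later. The documents do not support that:
- SAP 6 and 9.8 build recurrence from rhythm recordings adjudicated by the ECG core lab, with or without the CABANA Box. No route is described by which an undated visit-form report enters the endpoint.
- The conversion needs treatment within 1.26 days of randomization. The lag to drug start is not given. The note under Protocol 3.1 lets some patients continue recent drugs, which makes a lag near zero plausible for them but does not establish it generally.
- The rule can also lose true recurrences. A drug patient starting on day 5 is blanked to day 95; an undated recurrence on day 100, reported on day 110, would be placed on day 91.26 and dropped. The net direction is unknown.

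Even on the adverse assumption the size is modest. A log-rank simulation took 735 CABANA Box patients per arm (two thirds of 2,204/2), no true effect and 50% recurrence at 12 months. False early events in 1% of the drug arm gave a hazard ratio (ablation to drug) of about 0.99 and rejection in about 6% of runs, against about 5% with none. At 5% false events the figures were about 0.95 and 15%.

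It is also tempting to count an undated AF episode only if its whole reporting interval lies after blanking. That would itself differ by arm. For a month 6 interval of about days 91 to 182, a patient treated on day 0 would be counted, but one ablated on day 14 would not, although 182 − 104 = 78 of those 91 days follow blanking.

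**Conclusion.** The point holds as a defect of the stated rule. Under the protocol's own windows, an undated event can be timed up to about 31 days after its reporting visit at month 3 and 65 days at month 12, and the event rule is inconsistent with the censoring rule beside it. The intention-to-treat endpoints timed from randomization see mainly a shift in timing, common to both arms. The substantive exposure is in the supplementary on-treatment and per-protocol analyses, where a drug-arm event can be moved past a crossover ablation.

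The overshoot figures rest only on the documents; the mean lateness of 45 and 91 days assumes uniform event dates and on-time visits. No effect on a trial result can be computed, because the number of undated events is not given. It is likely small. An arm-specific bias in recurrent AF is not shown.

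**What to change.** In SAP 7.3, place an undated event between the last contact known to be event-free and the actual date of the reporting visit, for example at the midpoint, and never later than that visit. Use the nominal month only when the visit date is also missing, as the censoring rule already does. Count the contact made at crossover as a contact for this purpose. Keep the requirement that imputed dates precede death.

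For recurrent AF, state in SAP 9.8 that the date of the rhythm recording is used and that blanking is judged from each patient's own treatment start plus 90 days.

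The cost is a few sentences and a small programming change, with no new data. The imputed date remains an assumption within its interval: where an ablation falls between the last event-free contact and the reporting visit, the true order stays unknown. Reporting the number of undated events by arm and endpoint would show whether any of this matters.

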9.1 All-cause mortality (key secondary endpoint)

Endpoint Definition: Time from randomization until death.

For subjects who have not met this endpoint (and thus are censored observations), time from randomization until the subject's last follow-up contact will be used in the analysis.

Great effort will be made to gather mortality information on every randomized subject. For patients who withdraw consent or are lost to follow-up during the course of the trial, mortality databases such as the National Death Index, the Social Security Death Index, Ancestry.com, as well as any other sources of information or national registries, will be consulted in an effort to determine whether the subjects have died. Any subject found through one of these sources to have died will be considered to have met this key secondary endpoint even if not enough information is available for the CEC to classify the mode of death. Subjects for whom no vital status information can be found in these database searches will be censored at the time of their last follow-up contact.

Statistical Methods: The analysis of this key secondary endpoint will use the same methods as described for the primary endpoint in Section 8. Specifically, the log-rank test will be the primary analytic tool for statistically assessing mortality differences between the two randomized treatment strategies. A hazard ratio and 95% confidence interval summarizing the difference in outcome between the two randomized arms will be computed using the Cox model. The level of significance for the assessment of this endpoint will be $\alpha=0.05$. Also, Kaplan-Meier cumulative event rates will be calculated for each randomized arm as a function of time from randomization, and the estimated event probabilities will be displayed graphically.

Supplementary analyses of this secondary endpoint will be performed using the same methods described for the primary endpoint in Section 8.1.

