7.6.3 Criteria for Withdrawal of Subjects from Study

No subjects will be removed from the study, and attempts will be made to collect follow-up information for all subjects except those who specifically withdraw consent for release of such information.

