To provide an adequate number of patients in the trial that will be relatively robust under various assumptions regarding the control-arm event rates and the magnitude of the treatment benefit, 2,000-2,200 patients will be enrolled. With a minimum follow-up of 3 years (amounting to an average follow-up of approximately 5 years), 2,200 patients will provide 90% power for detecting a 30% reduction in the new primary endpoint, and 2,000 patients will provide 88% power, assuming a 3-year event rate in the drug arm of 12% and allowing for a 2% loss to follow-up. Thus, the study will have high power for detecting an important benefit if the control arm event rate is consistent with the rate expected based on previous studies. A sample size in this range will also provide acceptable power (86% with 2200 patients and 82% with 2000 patients) for detecting a 25% reduction with ablation in the primary endpoint if the 3-year drug arm event rate is 15%. Thus we will have good power for detecting a more conservative estimate of the benefit in the composite endpoint if the control arm event rate is higher, but still consistent with previous studies. A 25-30% reduction in primary events will be highly important from a clinical and public health standpoint, given the large population of patients in this country and throughout the world who suffer from AF.

This number of patients (2,000-2,200) will also provide adequate power for detecting a 25% reduction in other important secondary composite endpoints listed in section 2.2 such as the endpoints that involve cardiovascular hospitalization where the incidence is expected to be higher than for the primary endpoint.

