16.0 Study Closeout

The end of the trial is defined as the day of the official end of patient follow-up in the trial.

For clinical trial sites located in the EU, a declaration of the end of the clinical trial will be made according to the procedures outlined in Directive 2001/20/EC. For sites located in countries outside the EU, local regulations will be followed.

Upon completion of the study DCRI and/or their designee will notify the site of closeout and a study closeout visit will be performed. The DCRI monitor and/or their designee will ensure that the Investigator's regulatory files are up to date and complete, and that any outstanding issues from previous correspondences have been resolved. Other issues to be reviewed at the closeout visit include: discussing retention of study files, possibility of site audits, publication policy, and notifying the IRB of study closure.

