7.2 Disposition of Subjects

The disposition of subjects (number randomized, number who received the randomly assigned treatment, number of treatment crossovers, number of patients who withdrew consent, and number lost to follow-up) will be summarized overall and by treatment arm. The summary of treatment crossovers will distinguish the patients randomized to the drug arm who subsequently underwent catheter ablation (crossed over to ablation) during the course of their follow-up and the patients randomized to the ablation arm who never received an ablation. The distribution of the length of follow-up for the overall study population and for each randomized arm will be characterized in terms of percentiles (median, 25th, and 75th percentiles). The number and percentage of patients who had at least 3 years of follow-up, and at least 5 years of follow-up will also be tabulated and reported. Among patients in the drug arm who crossed over to ablation, the distribution of length of follow-up prior to the crossover will be described in terms of percentiles. Also the distribution of follow-up among patients who withdrew consent (i.e., patients who withdrew prior to the protocol-specified 3 years of follow-up) will be summarized in terms of percentiles. Additionally, the number and percentage of patients who withdrew consent before 3 years, after 3 to <5 years, and after 5 years will be tabulated.

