All possible events are carefully reviewed and adjudicated by a Clinical Events Committee (CEC) completely blinded to the randomized treatment assignment.

Endpoint Definitions: Detailed definitions for each of the events are outlined in the CEC charter. We note that a disabling stroke during follow-up must be documented by a neurologic evaluation or brain CT / MR studies and result in a disabling, irreversible physical limitation defined by a Rankin Stroke Scale ≥ 2 . Serious (or life-threatening) bleeding is considered to have occurred if intracranial bleeding or other bleeding occurs at any time during follow-up accompanied by hemodynamic compromise that requires surgical intervention or a transfusion of ≥ 3 units of blood. The serious bleeding definition *does not* include bleeding occurring with cardiac perforation or tamponade.

The time from randomization to the first event among the components of the primary composite endpoint will be measured (in days) for those who experienced an event and calculated as the date of the first event minus the date of randomization. For patients who do not experience any of the component events or who withdraw consent or drop out of the study before experiencing an event, time from randomization to the date of last contact will be used in the analysis, and those patients will be considered as censored observations in the time-to-event analysis. For

interim analyses, the best available endpoint data will be used (i.e., adjudicated data when available; otherwise site-reported event data).

Statistical Methods: The log-rank test¹ will be the primary analytic tool for statistically assessing outcome differences between the two randomized treatment strategies with respect to the primary composite endpoint. This analysis will be conducted using PROC LIFETEST in SAS. A hazard ratio (HR) and 95% confidence interval (CI) summarizing the difference in outcome between the two randomized arms will be computed using the Cox proportional hazards model² (PROC PHREG in SAS), using treatment as the only predictor in the model.

In addition to the statistical hypothesis testing, cumulative event rates will be calculated according to the method of Kaplan and Meier³ for each randomized arm as a function of time from randomization, and the estimated event probabilities will be displayed graphically.

The methods described above will constitute the primary analysis of this endpoint. The primary hypothesis is defined as:

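### SAP 9.1 counts database deaths found after withdrawal or loss but censors searched patients with no vital status at last contact, so censoring depends on the outcome; the effect is negligible at the documented 2% loss and modest at larger, assumed losses.

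*SAP*

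**What the plan says.** SAP 9.1 makes all-cause mortality the key secondary endpoint, analysed by log-rank test, Cox model and Kaplan-Meier at the 0.05 level. It sets three rules:

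- A subject without the endpoint is censored at last follow-up contact.
- Patients who withdraw or are lost are looked up in the National Death Index, the Social Security Death Index, Ancestry.com and other, unnamed sources or national registries. "Any subject found through one of these sources to have died will be considered to have met this key secondary endpoint".
- Subjects for whom "no vital status information can be found in these database searches will be censored at the time of their last follow-up contact".

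9.1 gives no last date for counting a database death. It does not say whether a registry record that a patient is alive counts as a contact.

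Related text:

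- SAP 7.2: the "number of patients who withdrew consent, and number lost to follow-up) will be summarized overall and by treatment arm", and "the number and percentage of patients who withdrew consent before 3 years, after 3 to <5 years, and after 5 years will be tabulated".
- Protocol 8.1 computes power "allowing for a 2% loss to follow-up". It does not say whether this includes withdrawals.
- Protocol 7.6.3 seeks follow-up information on all subjects "except those who specifically withdraw consent for release of such information".
- Protocol 16.0: "The end of the trial is defined as the day of the official end of patient follow-up in the trial".

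**The concern.** Take two patients lost at year 1. One is found in a database to have died at year 4 and contributes four years and a death. The other is not found and contributes one year. The analysis admits post-loss time because a death occurred in it, and drops the matching survival time. Kaplan-Meier, log-rank and Cox methods all assume that censoring carries no such information.

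At stake is the one designated key secondary endpoint, which was the trial's original primary endpoint. The trial is open-label, so withdrawal could differ by arm. The direction of any bias depends on which arm has more post-loss time, so the rule should be settled before results are known. Nothing elsewhere corrects it: SAP 7.3 deals with missing dates and SAP 8.1 with covariate adjustment.

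**Working it through.** **The plan's own figure.** SAP 9.1 states no number. The power statement that carries the 2% loss can be checked. With a 12% three-year drug-arm rate, the hazard is −ln(0.88)/3 = 0.0426 per year. Take HR 0.70, follow-up uniform over 3 to 7 years (mean 5) and 2,200 × 0.98 patients. This gives about 355 events, and power is Φ(√(355/4) × 0.357 − 1.96) = 91.9%, against the stated 90%. The other three stated values (88, 86 and 82%) come out at 89.3, 86.3 and 83.0%. The figure reproduces within two points, and the finding does not depend on it.

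**Inputs.**
- From the SAP: 2,204 patients randomized 1:1 (1,102 per arm); minimum follow-up just under 2 years, median about 4.
- From the protocol: 2% loss.
- Assumed, not in the documents: true HR 1; death hazard 2.5% per year; follow-up uniform over 2 to 6 years; search capture s = 90%; loss unrelated to risk and uniform over follow-up, unless stated.

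These give 1,102 × [1 − (e^−0.05 − e^−0.15)/0.1] ≈ 104 deaths per arm, about 208 in all, and SE(log HR) = √(4/208) = 0.139.

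**Formula.** Let f be the share of an arm's full person-time that falls after loss. With a fraction p lost at uniform times, f = p/2. The written rule keeps a fraction 1 − (1 − s)f of deaths but only about 1 − f of the time, so the death rate is inflated by about 1 + s·f. The null HR becomes about (1 + s·f_ablation)/(1 + s·f_drug).

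**At 2% in each arm.** f = 0.01. Inflation is 0.9 × 0.01 = +0.9%. Database deaths are 104 × 0.01 × 0.9 ≈ 0.9 per arm. By simulation, five-year mortality rises 0.11 points from a true 11.8%. HR is 1.000 when amount and timing match. If one arm loses its 2% in the first half of follow-up (f = 0.02 × 0.75 = 0.015) and the other in the second half (f = 0.005), HR is 1.0045/1.0135 = 0.991, or 1.009 with the arms exchanged. Loss of 1% against 3% gives the same two values of f and the same result.

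**At larger, assumed losses.** Simulation with 3 million patients per arm, true HR 1, uniform timing:

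| Capture | Loss, ablation/drug | As written | Cut-off censoring for all | Last contact for all |
|---|---|---|---|---|
| 90% | 5/10% | 0.978 | 1.003 | 1.000 |
| 90% | 5/15% | 0.955 | 1.005 | 1.000 |
| 60% | 5/10% | 0.985 | 1.010 | 1.000 |
| 60% | 5/15% | 0.970 | 1.021 | 1.000 |
| 30% | 5/10% | 0.992 | 1.018 | 1.000 |
| 30% | 5/15% | 0.984 | 1.038 | 1.000 |

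Hand check, 5/10% at 90%: (1 + 0.9 × 0.025)/(1 + 0.9 × 0.05) = 1.0225/1.045 = 0.978. Cut-off censoring keeps all the time but misses deaths, so its HR is [1 − (1 − s)f_ablation]/[1 − (1 − s)f_drug]. At 60% and 5/15% this is 0.99/0.97 = 1.021.

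**Scale.** |ln 0.978|/0.139 = 0.16 SE and |ln 0.955|/0.139 = 0.33 SE. At 1/3% loss the shift is about 0.06 SE.

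**Risk-related loss.** Suppose 30% of patients have triple the hazard and twice the loss. At 15% loss and 20% capture, the written rule gives a death rate of 0.0246 against a true 0.0245, so the overstatement has gone. Last-contact censoring then gives a null HR of about 1.005 to 1.012 for 5/10 to 5/15% loss. At 30% capture the written rule gives about 0.996 and 0.992, and cut-off censoring about 1.02 and 1.04.

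**The case against.** The strongest reply is that the only loss figure in the documents is 2%, where the shift is about 0.06 SE. Every larger number rests on assumed loss that is unequal, or timed differently, between arms. SAP 7.2 will report withdrawal and loss by arm and when withdrawals occurred, so readers could see an imbalance. This stands as to size. It does not remove the defect, because a table of losses does not correct the estimate. SAP 7.2 also counts withdrawals separately from loss, so the 2% may not cover everyone searched.

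A second reply is that the obvious cure, carrying every searched patient not found dead to a common cut-off, assumes survival for people whose status is unknown. 9.1 names three databases and leaves the rest to unspecified registries, while the protocol planned about 60 of 180 sites outside North America. Poor capture for some patients is plausible, and at 30% capture that cure does worse than the written rule. This stands in full and limits the fix.

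Three stronger readings are tempting but unsupported:

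- That the mortality HR in this trial is materially biased, or biased in favor of ablation. The documents give no loss by arm, so neither size nor direction is known.
- That mortality is always overstated in each arm. Risk-related loss with low capture can cancel the overstatement.
- That the primary composite is affected. In SAP Section 8, for patients who "withdraw consent or drop out of the study before experiencing an event, time from randomization to the date of last contact" is what enters the analysis, and 9.1 confines database deaths to the mortality endpoint. No change to Section 8 is needed.

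**Conclusion.** The point holds as a defect of the rule in SAP 9.1: after loss, censoring depends on the outcome, and no other passage corrects it. The effect is negligible at 2% loss. It reaches 0.16 to 0.33 SE only under assumed losses of 5/10 to 5/15% with 90% capture and uniform timing. With loss unrelated to risk, the HR is biased against the arm with more post-loss time, so equal percentages protect it only if timing and capture also match. The size in this trial cannot be determined from the documents. A change is worth making because it is cheap and because the direction would otherwise be learned only with the results.

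**What to change.** Change 9.1 only.

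1. Set one fixed cut-off date for counting deaths: the earlier of the end of patient follow-up (Protocol 16.0) and the date through which the searched databases are complete. Count no later death.
2. Where a patient was searched in a registry with near-complete death coverage and not found dead, censor at that cut-off. Censor patients confirmed alive at the confirmation date, not beyond the cut-off. For patients who could not be searched (for example under the exception in Protocol 7.6.3), or whose country has no such registry, censor at last contact and do not count later database deaths in that analysis.
3. Add a sensitivity analysis that censors every withdrawn or lost patient at last contact and ignores later database deaths. Report both.

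The cost is SAP wording and one further analysis; the searches are already planned. Some database deaths will be left out where coverage is poor. Incomplete capture biases cut-off censoring the other way, as the table shows, so it must not be applied to all patients. Last-contact censoring is slightly biased when loss is related to risk, which is why both results should be shown.
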